3.5. Analysis Timing and Unmasking

The analysis of data from the first 12 months of the study will be performed when all subjects have completed the Month 12 visit in the study or discontinued early and all corresponding data have been entered into the database, reviewed, cleaned, and finalized as the Month 12 dataset per the 12-Month Primary Analysis Data Cut Plan and the Programming Plan. At the time of the analysis of the Month 12 dataset, subjects who have not completed or discontinued from the study will still be followed by the sites as part of the second year.

At the time of the Month 12 reporting, Sponsor personnel who are analyzing, interpreting, and reporting data from the Month 12 dataset will be unmasked to treatment assignment. To maintain data integrity for the remainder of the study, sponsor and contract research organization (CRO) personnel responsible for continuing study oversight will remain masked as documented in the Study Masking Plan and the GA Internal Unmasking Plan.

Analyses will include formal hypothesis testing of the primary efficacy endpoint at Month 12. Key secondary, secondary, and exploratory endpoints will be evaluated based on the Month 12 dataset in a descriptive manner. An analysis of the safety data in the Month 12 dataset will also be performed.

The final study reporting will be based on data after all subjects have either completed the Month 24 visit in the study or discontinued the study early, and all data from the study are entered in the database and the database is reviewed, cleaned, and locked as the final dataset. Minor changes are expected from the Month 12 dataset (e.g. adverse event end dates for events ongoing in the Month 12 dataset), however, all subsequent differences in data prior to the Month 12 visit will be listed. Analysis of the final dataset will include testing of hypotheses of the key secondary endpoints at Month 24 as described in Section 6.3.1. A cumulative analysis of all data through the end of the study will be produced based on the final dataset.

Aggregate results of the Month 12 reporting may be reported before completion of the study. However, subjects, masked study site personnel, masked CRO personnel at Covance, Sponsor team members with study oversight responsibility, and central reading center personnel will remain masked to individual treatment assignments until after the study is completed

(after all subjects have either completed Month 24 or discontinued early from the study), the database is locked and the unmasking has been approved.

3.6. Definition of 12-Month Data in the Month 12 Dataset

All screening and post-baseline data with a clinical date (i.e., administration/assessment/onset/start date) on or before the defined Month 12 data cutoff date will be included in the Month 12 Dataset. The 12-month data cutoff will include all data regardless of the type of study visit at which it was collected. This may include data collected at unscheduled visits or early termination visits if the visit date was on or before the 12-month data cutoff date. The Month 12 data cutoff is defined as:

- If the subject completed Month 12 (Visit 14) assessments, then the data cutoff will be the day that the Month 12 (Visit 14) assessments are completed, regardless of Study Day.
- If the subject did not complete the Month 12 (Visit 14) assessments (e.g. missed or early terminated) then Study Day 375 (Study Day 360 (target date) + 15) will be used as the Month 12 cutoff.

4. STATISTICAL ANALYSIS SETS

Two sham treatment arms (SM and SEOM) will be pooled into a single control (Sham) group for analyses.

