**Table 1: Treatment Arms With Approximate Number of Subjects**

Treatment arms
Pegcetacoplan 15 mg/0.1 mL monthly for 24 months (n = approximately 200 subjects; 24 pegcetacoplan injections)
Pegcetacoplan 15 mg/0.1 mL every other month for 24 months (n = approximately 200 subjects; 12 pegcetacoplan injections)
Sham monthly for 24 months (n = approximately 100 subjects; 24 sham injections)
Sham every other month for 24 months (n = approximately 100 subjects; 12 sham injections)

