### 12.8. Safety Analyses

Adverse events will be collected from the time of the first study drug administration until a subject completes the study or discontinues prematurely. Treatment-emergent adverse events are defined as those AEs that develop or worsen after the first dose of study medication and up to 30 days beyond the last dose of study medication. The current version of MedDRA will be used to classify all AEs. Treatment-emergent AEs will be summarized by System Organ Class and Preferred Term, in accordance with the MedDRA coding dictionary. The number of subjects reporting each AE Preferred Term will be tabulated for all TEAEs and separately for those considered as related to study treatment by the investigator or designee. Number of subjects reporting SAEs will also be tabulated. Adverse event summaries will be presented for each treatment group separately.

Adverse events will be summarized by MedDRA coding terms, and separate tabulations also will be produced for related AEs (those considered by the investigator as definitively drug related), SAEs, and discontinuations due to AEs. Vital signs data and findings from physical and ophthalmologic examinations will be tabulated for changes over time on study. Laboratory parameters will be summarized for changes across study by using descriptive statistics. Separate summaries will be prepared for systemic (nonocular) and ocular AEs, with events in the study eye and nonstudy eye summarized separately.

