7.1. Adverse Events

AEs will be coded using the MedDRA version 23.1 and summarized separately for those occurred in the study eye, those in the fellow eye, and the non-ocular events.

An AE will be considered a TEAE if it has a start date on or after the first dose of investigational product or if it has a start date before the date of the first dose of investigational product but increases in severity on or after the date of the first dose of investigational product.

An overall summary of the number of subjects with TEAEs will be presented, including the number and percentage of subjects with:

- Any TEAEs
- TEAEs related to study drug (evaluated by the investigator as definitely related, possibly related)
- TEAEs related to study drug injection procedure
- All TEAEs by maximum severity
- Serious TEAEs
- Serious TEAEs related to study drug (evaluated by the investigator as definitely related, possibly related)
- Serious TEAEs related to study drug injection procedure
- Serious TEAEs by maximum severity
- TEAEs leading to interruption of study treatment
- TEAEs leading to discontinuation of study treatment
- TEAEs leading to study discontinuation
- TEAEs leading to death

This overall summary will also include the total number of TEAEs reported. This overall summary will also be summarized separately for those occurred in the study eye, those in the fellow eye, and the non-ocular events.

The number and percentage of subjects reporting TEAEs in each treatment group and overall will be tabulated by SOC and PT for all of the categories in the list above. If more than 1 AE occurs with the same preferred term for the same subject, then the subject will be counted only once for that preferred term using the most severe and most related occurrence for the summarization by severity and by relationship to investigational product.

Endophthalmitis and intraocular inflammation ocular TEAEs will be presented by PT for study eye and fellow eye.

Endophthalmitis and intraocular inflammation ocular TEAEs in the study eye will also be presented on a per-injection basis (i.e., number of events/total number of injections given).

All SOC and PT summaries will be ordered alphabetically by SOC and within SOC, by descending order of the total number of subjects in the PM, PEOM, and Sham groups combined.

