7.8. Immunogenicity

Immunogenicity data will be listed separately for anti-pegcetacoplan peptide antibody and anti-PEG antibody results. The number and percentage of samples confirmed positive for ADA response will be summarized by treatment groups (i.e., PM, PEOM, and Sham). The number and percentage of subjects with treatment-emergent and treatment-boosted responses will be presented by treatment group. Treatment emergent response is defined as a confirmed positive antibody result postdose after a negative antibody result reported at baseline. Treatment-boosted response is defined as a ≥ 4 -fold increase in titer from the baseline level.

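### Safety tables set both active arms against a pooled sham group matched to neither on procedures or visits, and no unpooled safety display is planned

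*SAP*

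**What the plan says.** The pooling rule opens SAP Section 4: "Two sham treatment arms (SM and SEOM) will be pooled into a single control (Sham) group for analyses". It carries no exception for safety, and SAP Section 1 says that the SAP supersedes the protocol's analysis plan.

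SAP Section 7 follows the rule. Section 7.1 orders the adverse event tables "by descending order of the total number of subjects in the PM, PEOM, and Sham groups combined", and Section 7.8 has immunogenicity "summarized by treatment groups (i.e., PM, PEOM, and Sham". Analyses with the two sham arms kept apart appear only for efficacy (SAP 6.2.3.2 and 6.3.3).

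Protocol Table 1 gives the planned procedures: PM "n = approximately 200 subjects; 24 pegcetacoplan injections", PEOM "n = approximately 200 subjects; 12 pegcetacoplan injections", and for the less frequent sham arm "Sham every other month for 24 months (n = approximately 100 subjects; 12 sham injections". Monthly sham has 24 procedures, also in about 100 subjects.

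Protocol Section 12.8 reads differently: "Adverse event summaries will be presented for each treatment group separately". The protocol states sham pooling for the ITT set (12.6) and the primary analysis (12.7.1), not for safety. SAP Section 15, which lists departures from the protocol, does not mention safety pooling.

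SAP 7.1 counts subjects with "TEAEs related to study drug injection procedure" as numbers and percentages. Only endophthalmitis and intraocular inflammation in the study eye are also shown per injection.

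**The concern.** The share of subjects with at least one procedure-related event rises with the number of procedures. The share with a finding made at a visit rises with the number of visits. A control group that mixes two regimens has an intermediate exposure that matches neither active arm.

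Three outputs are exposed:

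- **Procedure-related study-eye TEAEs (SAP 7.1).** Sham follows the active procedure up to the injection itself (Protocol 7.4), and procedure-related events were the most frequent in Phase 2 (Protocol 4.1.4).
- **IOP above 21 or 30 mmHg (SAP 7.5).** Incidence is reported over the whole study, so more visits and procedures give more chances to cross a threshold.
- **Exudative AMD (SAP 7.1.1).** In Year 2, SD-OCT is monthly in the monthly arms and every other month in the others (SAP Tables 9 and 11). This was the main Phase 2 imbalance: 18 PM and 7 PEOM cases against 1 of 81 on sham.

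For PEOM the mismatch runs in the unsafe direction, because a control with more procedures and visits can mask part of a real excess.

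**Working it through.** **Reproducing the planned counts.** Monthly dosing on Day 1 and Months 1 to 23 gives 1 + 23 = 24. Every-other-month dosing on Day 1 and Months 2, 4, …, 22 gives 1 + 11 = 12. Both agree with Protocol Table 1. Before Month 12 the counts are 12 and 6, the denominators used in SAP 5.6. (The schedule for the monthly group in Protocol Appendix B appears to mark an administration at Month 24, which Section 8.1.4.2 excludes. The count here follows Table 1; the passages must be reconciled.)

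**Visits.** Scheduled post-baseline visits, leaving out the Day 7 sampling visit, are 12 in Year 1 for everyone, then 12 (monthly) or 6 (every other month) in Year 2. The totals are 24 and 18.

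**Pooled sham**, with the two sham arms at about 100 each:

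- procedures over 24 months: (100 × 24 + 100 × 12) / 200 = 18
- procedures before Month 12: (100 × 12 + 100 × 6) / 200 = 9
- visits over 24 months: (24 + 18) / 2 = 21

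**Ratios to pooled sham.** Procedures: PM 24/18 = 1.33, PEOM 12/18 = 0.67, with the same ratios at Month 12 (12/9 and 6/9). Visits: 24/21 = 1.14 and 18/21 = 0.86. Against the regimen-matched sham arm every ratio is 1.00.

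**Size of the artefact.** Assume a constant, independent per-procedure risk p, equal in active and sham. Incidence after k procedures is 1 − (1 − p)^k, and pooled sham is the mean of the k = 24 and k = 12 values. The documents give no p, so a range is shown for 24 months:

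| p | k = 24 | k = 12 | Pooled sham | PM − pooled | PEOM − pooled |
|---|---|---|---|---|---|
| 0.25% | 5.8% | 3.0% | 4.4% | +1.4 | −1.4 |
| 0.5% | 11.3% | 5.8% | 8.6% | +2.7 | −2.7 |
| 1% | 21.4% | 11.4% | 16.4% | +5.0 | −5.0 |

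At Month 12 (k = 12 and 6) the same risks give about 0.7, 1.4 and 2.8 points each way.

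**Unequal risks.** The artefact is the pooled sham incidence minus the matched sham incidence, which is half the SM–SEOM difference. It therefore depends on the sham risk alone. Take an assumed 0.5% for active and 0.1% for sham:

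- Incidences are PM 11.3%, PEOM 5.8%, SM 2.4%, SEOM 1.2% and pooled sham 1.8%.
- The PM gap is 9.6 points against pooled sham and 9.0 against SM.
- The PEOM gap is 4.1 points against pooled sham and 4.6 against SEOM.

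The direction is unchanged and the size is about 0.6 points.

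**Precision cost of matching.** At 10% incidence the standard error of a risk difference is √[0.09 × (1/200 + 1/200)] = 3.0 points against pooled sham and √[0.09 × (1/200 + 1/100)] = 3.7 points against one sham arm. For an event not seen in control, the one-sided 95% upper bound is 1 − 0.05^(1/200) = 1.5% or 1 − 0.05^(1/100) = 3.0%.

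**The case against.** The strongest objection is that sham and active do not share a per-procedure risk. Protocol 7.4 has only the blunt end of the syringe touch the eye in the sham arms; nothing enters it. A reader might infer from the unmatched exposure that, with no drug effect, PEOM would look safer than sham. Approximately, that needs 12 × active risk < 18 × sham risk, so a sham risk above two thirds of the active risk. Events caused by the needle need not meet that condition, and in the unequal-risk case above PEOM still looks worse than pooled sham. This stands. The reading fits only events from shared preparation steps or visit-based detection.

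The plan also has partial remedies. SAP 5.6 reports total injections by group, SAP 7.1 gives per-injection figures for two event types, and SAP 7.1.1 gives subject-year rates and Kaplan-Meier output for exudative AMD. The per-injection figures do answer the procedure mismatch for those two event types. Subject-year rates do not, because planned follow-up is 24 months in every arm, and Kaplan-Meier curves do not equalise how often the eye is imaged.

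Visit frequency is the same on schedule in Year 1, apart from the COVID-19 allowance that every-other-month subjects may skip non-dosing visits (Protocol Appendix K). Scheduled angiography is identical across regimens, and the slit-lamp and ophthalmoscopy shift tables use fixed visits. This limits the detection argument mainly to Year 2 SD-OCT and whole-study IOP thresholds.

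Safety output is descriptive, so no type I error is at stake, and pooling is a defensible precision choice for rare events. Finally, table shells are not part of these documents. Protocol 12.8, and the SAP 4.4 rule that assigns misdosed subjects by regimen, leave some doubt about the final layout. SAP 4, 7.1 and 7.8 nevertheless point to one sham column.

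**Conclusion.** The point holds as a mismatch in a defined set of safety displays. Against pooled sham, PM has 1.33 times and PEOM 0.67 times the planned procedures, with a smaller imbalance in visits that arises in Year 2. For procedure-related study-eye TEAEs, whole-study IOP threshold incidence and Year 2 OCT-detected exudation, the comparison tends to overstate the excess for PM and understate it for PEOM. The 1.4 to 5.0 points at 24 months rest on an assumed equal risk of 0.25% to 1% per procedure and on constant, independent risk with no missed procedures. The figure is smaller where the sham risk is lower, and systemic events are little affected.

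Two stronger readings are not supported. The twofold difference lies between the two sham arms, not between an active arm and its control. And the documents do not show that the overall safety conclusion is biased, or that safety comparisons as a whole should rest on matched controls of about 100; that would give up precision where rare events need it. The gap between Protocol 12.8 and SAP Section 4, unrecorded in SAP Section 15, stands without any modelling assumption.

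**What to change.** Keep the pooled Sham column, which serves rare events best. Add SM and SEOM columns beside it in SAP 7.1 (study-eye and injection-procedure TEAEs), in 7.1.1, and in the IOP threshold table of 7.5, so that PM against SM and PEOM against SEOM can be read directly. List safety pooling in SAP Section 15 as a departure from Protocol 12.8.

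The cost is two extra columns in those tables and no new data. Matched comparisons will be less precise, with a standard error of 3.7 rather than 3.0 points at 10% incidence and a zero-event upper bound of 3.0% rather than 1.5%. That is why the added columns should supplement the pooled display and not replace it.

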4.1. Screened Set

The screened set consists of all subjects who provided written informed consent and are screened for participation in this study. This population will only be used for the purposes of describing the subject disposition and for listing the data.

4.2. Intent-to-Treat Set

The Intent-to-treat (ITT) set consists of all randomized subjects. Subjects will be analyzed in the treatment arm assigned at randomization.

4.3. Modified Intent-to-Treat Set

The modified ITT (mITT) set consists of all randomized subjects who receive at least one injection of pegcetacoplan or sham and have baseline and at least one post-baseline value of GA lesion area in the study eye as assessed by FAF. Subjects will be analyzed in the treatment arm assigned at randomization.

4.4. Safety Set

The Safety set consists of all subjects randomized who receive at least one injection of pegcetacoplan or sham. Subjects will be analyzed according to the actual treatment received. In the case a subject received an incorrect injection of study medication than what they were randomized to, subjects will be presented under the corresponding pegcetacoplan arm if they received at least one injection of pegcetacoplan during the study and will only be presented under the corresponding sham arm if they did not receive any injections of pegcetacoplan. This population will be used for all safety analyses.

4.5. Per-Protocol Sets

The Per-Protocol (PP) sets will be identified separately for Month 12 and Month 24 analysis, respectively (i.e., Month 12 PP set and Month 24 PP set). The PP sets consist of all mITT subjects who have a valid GA lesion area assessment for either Month 10 or 12 (Month 12 PP set) or a valid GA lesion area assessment for at least one of Month 18, 20, 22, 24 (Month 24 PP set) and who follow the protocol without any major deviation(s) that could affect the primary efficacy data.

A valid GA lesion area assessment is defined as a non-missing measured GA lesion area assessment at a given timepoint where at least 75% of the expected injections over the course of participation ahead of the given timepoint have been received by the subject. For example:

- A valid GA lesion measurement at Month 10 in the Monthly arm would be a result available at Month 10 with no more than 2 missed injections prior to the Month 10 assessment (10 scheduled before Month 10, 2 missed = 80% compliance).

- A valid GA lesion measurement at Month 20 in the every other month (EOM) arm would be a result available at Month 20 with no more than 2 missing injections prior to the Month 20 assessment (10 scheduled before Month 20, 2 missed = 80% compliance).

Major protocol deviations (PDVs) that lead to exclusion from the Month 12 PP set and the Month 24 PP set are as follows:

(i) Violations of inclusion and/or exclusion criteria

A PDV with any of the following inclusion and/or exclusion criteria violations will be classified as a major PDV:

Inclusion Criterion #3: Clinical diagnosis of GA of the macula secondary to AMD as determined by the Investigator and confirmed by the Reading Center

Inclusion Criterion #4: The GA lesion must meet the criteria listed in the protocol as determined by the central Reading Center's assessment of FAF

- Total GA area must be ≥ 2.5 and ≤ 17.5 mm² (1 and 7 disk areas [DA] respectively).
- If GA is multifocal, at least one focal lesion must be ≥ 1.25 mm² (0.5 DA), with the overall aggregate area of GA as specified above in 4a.
- The entire GA lesion must be completely visualized on the macula centered image and must be able to be imaged in its entirety and not contiguous with any areas of peripapillary atrophy.
- Presence of any pattern of hyperautofluorescence in the junctional zone of GA. Absence of hyperautofluorescence (i.e., pattern = none) is exclusionary.

Exclusion Criterion #1: GA secondary to a condition other than AMD such as Stargardt disease, cone rod dystrophy or toxic maculopathies like plaquenil maculopathy in either eye.

Exclusion Criterion #3: Any history or active choroidal neovascularization (CNV), associated with AMD or any other cause, including any evidence of retinal pigment epithelium rips or evidence of neovascularization anywhere based on spectral domain optical coherence tomography (SD-OCT) imaging and/or fluorescein angiography as assessed by the Reading Center.

Exclusion Criterion #13: Prior participation in another interventional clinical study for geographic atrophy in either eye including investigational oral medication and placebo.

(ii) Not receiving assigned treatment

Not receiving assigned treatment at more than 25% of the treatment visits over the analysis timeframe, either 12-month or 24-month, will be classified as a major PDV.

4.6. Pharmacokinetic Set

The PK set will include all subjects in the safety set who have at least one quantifiable post-dose concentration of pegcetacoplan (even with values below the limit of quantification (BLQ)).

4.7. Pharmacodynamic Set

The pharmacodynamic (PD) set will include all subjects in the safety set who have at least one quantifiable post-dose PD endpoint (C3, CH50, or AH50) evaluated.

4.8. Genotyping Set

The genotyping set consists of all ITT subjects who have at least one non-missing genotyping result for a single nucleotide polymorphism (SNP) associated with age-related macular degeneration from the genotype sequencing analysis.

5. STUDY SUBJECTS

5.1. Disposition of Subjects

The number of subjects screened, passed screening, screened failed, and the reasons for screen failure will be presented overall.

The number of subjects randomized and in each defined analysis set will be summarized by treatment group and overall for the ITT Set. In addition, the reasons for exclusion from the mITT and per-protocol populations will be summarized.

Subjects' disposition by region and country will also be provided for the ITT set. All summaries on subject disposition will be produced based on the Month 12 dataset for the Month 12 reporting and based on the final study dataset for the final reporting, as appropriate.

Overall summary of subjects' disposition includes:

- Number of subjects randomized
- Number of subjects completed treatment [through Month 12 or Month 24, as appropriate]
- Number of subjects discontinued from treatment and reason for discontinuation [prior to Month 12 or Month 24 as appropriate]
 - Subjects who discontinued from treatment without concurrent study discontinuation will be singled out [prior to Month 12 or Month 24 as appropriate]
- Number of subjects completed study [through Month 12 or Month 24, as appropriate]
- Number of subjects discontinued from study and reason for discontinuation [prior to Month 12 or Month 24 as appropriate]

A summary of the disposition through each study visit will also be presented by treatment group and overall for the ITT set.

In addition, to assess the impact of COVID-19 pandemic on disposition of subjects, the following summary will be provided for each study visit and by reason (COVID-19 vs. non-COVID-19) for the ITT set:

- Number of subjects discontinued from treatment
- Number of subjects discontinued from study

